### **Objectives**

Primary Objective:

Compare amount of intravenous (IV) opioid consumption within 24-hour period amongst laparoscopic sleeve gastrectomy patients who receive the unilateral ultrasound-guided subcostal TAP block with bupivacaine to those who receive the block with only sterile saline.

Secondary Objectives:

- a. Amount of intraoperative IV opioid consumption
- b. Amount of post-operative IV opioid consumption
- c. Severity of pain at rest using an 11-point numeric pain score Likert scale at 1, 6, 12 and 24-hour marks postoperatively
- d. Time to breakthrough pain after surgery
- e. Area of pain after surgery
- f. Presence of postoperative nausea (yes/no) at 1, 6, 12 and 24-hour marks postoperatively
- g. Time to ambulation after surgery
- h. Analgesia satisfaction score at end of hospital stay
- i. Hospital length of stay

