### **Duration of Participation**

Individual participation in this study will conclude following discharge from the hospital after laparoscopic gastrectomy surgery. Duration of participation will depend on the length of hospitalization. Typical duration of stay for this type of surgery is usually 1–3 days.

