### **Procedures for Investigators to Withdraw Subjects**

The patient will be informed if they need to be withdrawn from the study. Should this decision be made prior to the procedure, the patient will undergo the surgery as per current standard of care; they will not be included in the experimental protocol. If this is decided following surgery, post-operative data collection will stop. Regardless, subjects will receive current standard of care. Collected PHI will be destroyed at the time of withdrawal.

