### **Description of Study Design**

Patients who are eligible for this subject will be invited to participate. Written informed consent will be obtained from eligible volunteers for this study.

This study will be a double-blinded randomized control trial. Patients will be randomized into one of two groups. Patients in Group 1 will undergo general anesthesia with a post-induction, post-intubation, pre-procedural subcostal TAP block with 40 mL 0.25% bupivacaine on the ipsilateral side as the extraction site. Patients in Group 2 will undergo general anesthesia with a post-induction, post-intubation, pre-procedural subcostal TAP block with 40 mL sterile normal saline on the ipsilateral side as the extraction site. Investigators will be blinded to the randomization of these patients. Following performance of these blocks, patients will receive standard care for the surgery as well as during the postoperative recovery period. Data will be obtained from the EPIC electronic medical record, and from the anesthesia computer record. Patients will be asked postoperatively to assess items such as their nausea and pain scores. Patients will also be contacted by phone within 1-2 days of discharge to obtain analgesic satisfaction scores. This data will be collected on the Redcap server.

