### **Description of Procedures being Performed**

Group allocation and instructions on preparing the injectate solution for the subcostal TAP block will be included in a sealed envelope. On the day of the surgery, the group allocation will be

revealed to an anesthesiologist not involved with the research study. The anesthesiologist will prepare the solution to be used for the subcostal TAP block.

Standard ASA monitors will be applied to all patients. A preoperative intravenous line will be placed. Patients will undergo standard induction with IV propofol, fentanyl and rocuronium. All study patients will receive 1.5mcg/kg of IV fentanyl on induction. Following induction, a subcostal TAP block will be performed on the ipsilateral site as the extraction site. Patients will be positioned in the supine position. A linear ultrasound probe will be parallel to the lower margin of the rib cage. The rectus abdominis muscle, posterior rectus sheath, and transversus abdominis muscle are identified on the ultrasound. A block needle will be advanced using an in-plane approach from medial to lateral, targeting the fascial plane between the posterior rectus sheath and the transversus abdominis muscle. For group 1 patients, 40mL of 0.25% bupivacaine will be deposited in this fascial plane. For group 2 patients, 40mL of normal sterile saline will be used instead.

General anesthesia will be maintained with inhalational anesthetic gas. Boluses of fentanyl will be given to all patients for pain control as needed, regardless of which group they are assigned to. Patients will also receive muscle relaxants for surgical relaxation as needed. Standard intravenous antiemetics, 8mg ondansetron and 10mg dexamethasone, will be given at the end of the surgery prior to extubation, unless otherwise contraindicated. Surgeons will use local anesthetic to subcutaneously infiltrate the other port sites. Following extubation, patients will recover in the post-anesthesia care unit (PACU) and then to the general hospital floor. Patients will be given scheduled intravenous acetaminophen 1000 mg and ketorolac (30 mg), as well as PRN intravenous opioids, i.e. fentanyl, hydromorphone.

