#### **Description of Data that Will be Collected Including Long-Term Follow-Up**

Data collected includes age, gender, BMI, ASA status, duration of surgery, total opioid use in PACU, total opioid consumption in 24 hours, severity of pain at rest on a Likert scale (0-10) and presence of postoperative nausea (yes/no) at 1 hour, 6 hours, 12 hours and 24 hours postoperatively, time to breakthrough pain after surgery, area of pain after surgery, time to ambulation after surgery, analgesia satisfaction score at time of discharge, and hospital length of stay.

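### When an investigator withdraws a patient after surgery, the protocol stops collecting the 24-hour opioid primary, although inpatient doses remain readable from the chart

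*Protocol*

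**What the plan says.** The section Procedures for Investigators to Withdraw Subjects covers patients whom the study team takes out. For a decision made after the operation: "If this is decided following surgery, post-operative data collection will stop". It then adds: "Collected PHI will be destroyed at the time of withdrawal". Standard care continues. The section names no grounds for withdrawal and does not exempt the primary endpoint or data read from the chart.

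The primary objective (Objectives) is: "Compare amount of intravenous (IV) opioid consumption within 24-hour period". The data list (Description of Data that Will be Collected) includes "total opioid use in PACU, total opioid consumption in 24 hours". The start of the 24-hour clock is not defined.

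On sources, Description of Study Design says: "Data will be obtained from the EPIC electronic medical record, and from the anesthesia computer record". Summary of Study Design places the post-operative opioid amount under EPIC and the intraoperative amount under Compurecord. Duration of Participation says: "Typical duration of stay for this type of surgery is usually" 1 to 3 days.

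The protocol's data analysis section says only who will do the analysis. The SAP lists tests and regression models. It defines no analysis population and gives no rule for incomplete 24-hour totals.

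**The concern.** A randomised comparison is protected when every randomised patient contributes an outcome in the allocated arm. Here the protocol's own rule can remove part of the primary outcome after randomisation and after study treatment, without any request from the patient. The missing part needs no interview or visit, because it is a medication record that the hospital keeps anyway.

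Two things could follow. A truncated total might be analysed as if complete, which understates that patient's use. Or the patient might be dropped, which makes the analysis a complete-case one. The plan does not say which. If the reason for withdrawal were related to opioid use, either route could distort the comparison.

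Withdrawal at the patient's own request has a similar stop rule in its own section. Consent may properly limit collection there, and this point does not extend to it.

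**Working it through.** **Text check.** The plan gives no figure to reproduce, so the passages are set side by side.

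1. *Timing of treatment.* The block is given after induction and intubation and before the procedure (Description of Study Design; Description of Procedures being Performed). A patient withdrawn after surgery has therefore normally been randomised and treated.
2. *Timing of the endpoint.* On any reading in which the 24-hour window runs past the end of surgery, a withdrawal before it closes stops collection part-way. Use from then to the end of the window is missing.
3. *Availability.* Care continues after withdrawal, and post-operative opioid use is an EPIC item. With a usual stay of 1 to 3 days, the chart normally covers most or all of the window. For a patient discharged before the window closes, it covers inpatient use up to discharge only.
4. *Later withdrawal.* If the decision comes after the window closes, the stop rule costs the primary nothing. Loss would then depend on whether the destruction sentence reaches outcome values, which the text leaves open.
5. *Repair elsewhere.* Neither the protocol's analysis section nor the SAP keeps these patients in the analysis.

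**Illustration only.** This is a complete-case scenario under an assumed mechanism in which high users are the ones withdrawn. The documents support neither the mechanism nor any input. It shows what it would take for the rule to matter.

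Assumptions: opioid use in SD units, saline N(0, 1), bupivacaine N(−d, 1). A fraction f of patients above a common threshold c is withdrawn before 24 hours and dropped. c is 1.645 (top 5% of saline) or 1.282 (top 10%). For an arm with mean μ, let p = 1 − Φ(c − μ). Then

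retained mean = [μ − f(μp + φ(c − μ))] / (1 − fp).

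Worked case, d = 0.5, c = 1.645, f = 0.25:
- Saline: p = 0.0500, φ = 0.1031, mean = −0.25 × 0.1031 / (1 − 0.0125) = −0.0261.
- Bupivacaine: p = 0.0160, φ = 0.0400, mean = [−0.5 − 0.25(−0.0080 + 0.0400)] / (1 − 0.0040) = −0.510.
- Difference 0.484 in place of 0.5, a shrinkage of 3.2%.

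| f (d = 0.5) | Difference, top 5% | Shrinkage | Difference, top 10% | Shrinkage |
|---|---|---|---|---|
| 0.10 | 0.4936 | 1.3% | 0.4905 | 1.9% |
| 0.25 | 0.4839 | 3.2% | 0.4756 | 4.9% |
| 0.50 | 0.4673 | 6.5% | 0.4492 | 10.2% |
| 1.00 | 0.4321 | 13.6% | 0.3898 | 22.0% |

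Over d = 0.3 to 0.8, shrinkage is 2.6–5.3% at f = 0.25 and 11–25% at f = 1.

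Simulated power (two-sided pooled t test at 5%, d = 0.5, 100,000 trials per cell; arm sizes assumed; each pair is top 5% / top 10%):

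| Per arm | No loss | f = 0.25 | f = 1 |
|---|---|---|---|
| 20 | 33.8% | 32.7% / 31.7% | 29.3% / 25.8% |
| 40 | 59.9% | 58.1% / 57.1% | 52.5% / 47.1% |
| 60 | 77.4% | 76.0% / 74.6% | 70.0% / 63.8% |

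With 40 per arm and f = 0.25, expected loss is 40 × 1.25% = 0.5 to 40 × 2.5% = 1.0 saline patients, and 40 × 0.40% = 0.16 to 40 × 0.94% = 0.38 bupivacaine patients. With no true effect and a common threshold, rejection stays at 4.9–5.1%, so the scenario shows no inflation of false positives.

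**The case against.** The strongest reply is that the documents describe no situation in which the rule would do harm. No ground for withdrawal mentions opioid use, and high use is provided for in the plan: "Boluses of fentanyl will be given to all patients for pain control as needed", in both groups, with as-needed IV opioids after surgery as well. Blinding also limits selective removal by arm: "Investigators will be blinded to the randomization of these patients". The illustration rests wholly on assumed inputs. It deletes patients where the defect is a partial total, it selects on a 24-hour value not yet known at withdrawal, and it uses Normal data although the SAP allows a Mann-Whitney test. All of this stands. It limits what can be said about consequence, but it does not remove the stop rule.

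It is also fair that the lack of an analysis population is a general gap in the SAP, and that the consent pages are not available here and may say something about chart use after withdrawal. The first adds no weight to this point; the second leaves the need for a consent change open.

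A reader might infer more than the text supports in three places:
- *That investigators may withdraw patients at will.* The section speaks of patients who need to be withdrawn. The reasons are unstated, but that does not establish free discretion.
- *That EPIC always holds the full 24-hour total.* It holds inpatient doses until discharge.
- *That the destruction sentence erases outcome values.* The sections on destroying PHI and on storing data treat the two separately, and other sections refer to de-identified data, which favours identifiers only. But opioid amounts are listed as health information, and age, sex, BMI and ASA status are listed as PHI. The text does not settle it.

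**Conclusion.** The point holds and is minor. As written, the rule leaves the primary endpoint incomplete for any patient whom an investigator withdraws after surgery and before the 24-hour window closes. That loss is avoidable up to discharge, and it does not arise from the patient revoking consent.

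Its consequence is unknown. Without a sample size, a withdrawal rate or a stated link between withdrawal and opioid use, neither the size nor the direction of bias can be estimated. If such withdrawals are rare or unrelated to outcome, the effect is negligible. Under the assumed high-use mechanism with patients dropped, a 0.5 SD effect would shrink by 3–5% if a quarter of the highest users were withdrawn. It would shrink by 14–22% only if all of them were. A reader might infer from those figures that the trial is biased, or biased toward the null. The documents support neither inference. The case for acting is that the repair is cheap, not that damage has been shown.

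**What to change.** In Procedures for Investigators to Withdraw Subjects, separate ending study participation from ending data collection. State that after an investigator withdrawal, chart-based opioid data continue to be extracted and kept to 24 hours, or to discharge if that is earlier, unless consent is invalid or revoked. Reword the destruction sentence so that it does not erase those outcome values.

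In the SAP, state that these patients are analysed in their allocated arm, and report withdrawals by arm with reasons so that readers can see whether loss was differential.

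Cost: protocol and SAP wording, possibly consent wording, and IRB review. No added visit or procedure is needed, because post-operative opioid use is read from existing records.

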### **How Participants will be Identified**

Patients scheduled for laparoscopic gastrectomy procedure with [name] and [name] will be identified at their preoperative surgical visit. The surgery team will discuss the study and provide written information/consent for the patient to review. Approximately 1 week prior to the surgery, a member of the research team will call the patient to discuss the study further and address any additional questions or concerns. They will also discuss the study in detail, confirm understanding, and review the consent form with the patient. If the patient agrees to the procedure, they will sign the consent on the day of surgery in the GP2 preoperative waiting area or in the GP3 holding area.

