## **Eligibility Criteria**

### **Inclusion Criteria:**

- Adults 18-80 years old
- Candidate for general anesthesia
- Undergoing laparoscopic sleeve gastrectomy
- Patients of participating surgeons

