Effect of Unilateral Ultrasound-Guided Subcostal Transversus Abdominis Plane Block in Patients Undergoing Laparoscopic Sleeve Gastrectomy

PI: [name]
NCT03856788
Document Date: Aug 24, 2022

Statistical Analysis Plan

Baseline descriptive statistics will be performed for demographic variables, intraoperative data, and for potential confounders. All variables will be checked for normality via Kolmogorov–Smirnov test or Shapiro–Wilk test as well as histogram visual inspection. Normal variables will be reported as mean, standard deviation, non normal variables will be reported as median [IQR]. Proportions will be reported as n(%) and analyzed via Chi Square test. Normal continuous variables will be analyzed via t test, or paired t-test depending on the variable. Non-normal variables will be tested via Mann-Whitney U test. Area-under the curve analyses will be evaluated through ROC analysis or other tests as indicated. Where applicable, linear or logistic regression will be utilized to assess for associations of variables for both univariate and multivariate analysis.

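### At least two surgeons operate and infiltrate port sites, but surgeon is neither a listed variable nor a prespecified covariate, which costs some precision and leaves the estimate open to chance imbalance

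*Protocol*

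**What the plan says.** **Surgeons.** The protocol's inclusion criteria require "Patients of participating surgeons", in the plural. The section on identifying participants says: "Patients scheduled for laparoscopic gastrectomy procedure with [name] and [name] will be identified at their preoperative surgical visit". The names are removed, but two are given. Neither the total number of surgeons nor their shares of cases is stated.

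**What the surgeon does.** Under Description of Procedures being Performed: "Surgeons will use local anesthetic to subcutaneously infiltrate the other port sites". The Summary of Study Design repeats this. Neither place gives agent, concentration or volume.

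**Randomization.** Under Description of Study Design: "Patients will be randomized into one of two groups". The mechanism follows in the procedures section: "Group allocation and instructions on preparing the injectate solution for the subcostal TAP block will be included in a sealed envelope". No blocking, stratification or surgeon-specific envelope set is mentioned.

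**Data.** The main list begins: "Data collected includes age, gender, BMI, ASA status, duration of surgery, total opioid use in PACU, total opioid consumption in 24 hours". Surgeon is not in the rest of that list, in the list of health information to be recorded, or among the EPIC and Compurecord items in the Summary of Study Design.

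**Analysis.** The SAP states: "Normal continuous variables will be analyzed via t test, or paired t-test depending on the variable", with Mann-Whitney U for non-normal variables. It adds that linear or logistic regression will be used where applicable and that potential confounders will be described at baseline. It names no covariate and does not tie the regression to the primary outcome.

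**The concern.** Surgeon is known before randomization, so it is a legitimate baseline covariate. The protocol itself supplies a route from surgeon to outcome. In a trial of bupivacaine against saline with 24-hour IV opioid consumption as the primary outcome, each surgeon adds local anesthetic of an unstated kind and amount. If surgeons differ in how they do this, opioid use may differ by surgeon within both arms.

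Two things are then at stake. First, variation between surgeons that could be explained stays in the error term, which widens the confidence interval. Second, in a small trial the arms may by chance contain different mixes of surgeons, which moves the observed difference in that one trial. The SAP leaves room for an adjusted analysis but leaves the choice of covariates until after the data are seen.

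**Working it through.** The documents give no sample size, alpha, power, effect size or SD, so there is no figure to reproduce. Everything below is illustration on assumed inputs.

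**Assumptions.** Two surgeons with half the cases each (q = 0.5); total N of 40 to 100; 1:1 allocation; a surgeon difference s of 0.3, 0.5 or 0.8 within-surgeon SD; two-sided alpha 0.05; 80% power when surgeon is in the model.

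**1. Chance imbalance.** Exact probability that the share of patients from one surgeon differs between arms by 20 percentage points or more, ties at 20 included. Simple randomization uses two independent binomials; equal arms use the hypergeometric distribution.

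| N | Simple 1:1 | Equal arms |
|---|---|---|
| 40 | 26.8% | 34.3% |
| 60 | 15.5% | 19.6% |
| 80 | 9.3% | 11.7% |
| 100 | 5.7% | 7.1% |

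With a 70/30 case split and equal arms the figures fall to 30.1%, 15.8%, 8.7% and 4.9%.

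**2. Shift in the estimate at a 20-point imbalance.** Shift = 0.20 × s:
- s = 0.3: 0.06 SD
- s = 0.5: 0.10 SD
- s = 0.8: 0.16 SD

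For comparison, the difference detectable with 80% power is √(2/n) × (1.960 + 0.842), with n per arm. At N = 40 (n = 20) this is 0.316 × 2.802 = 0.89 SD. At N = 100 (n = 50) it is 0.200 × 2.802 = 0.56 SD. The shift therefore runs from 0.06/0.89 = 7% to 0.16/0.56 = 29% of a detectable effect.

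**3. Precision.** Leaving surgeon out multiplies the error variance by 1 + s²q(1−q). The share of outcome variance due to surgeon is s²q(1−q) / [1 + s²q(1−q)]. Unadjusted power is Φ(2.802/√inflation − 1.960).

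| s | Variance inflation | Share of variance | Unadjusted power |
|---|---|---|---|
| 0.3 | 1.0225 | 2.2% | 79.1% |
| 0.5 | 1.0625 | 5.9% | 77.6% |
| 0.8 | 1.16 | 13.8% | 73.9% |

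Against 80% with adjustment, the loss is 0.9 to 6.1 points.

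**4. Type I error.** 20,000 simulated null trials, N = 60, equal arms, s = 0.8:
- Allocation ignoring surgeon, unadjusted t test: 0.049.
- Allocation stratified by surgeon, unadjusted t test: 0.036.

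The unadjusted test is valid when allocation ignores surgeon. Stratifying without adjusting makes it conservative, so the precision gained by balancing is not used.

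**The case against.** The strongest reply is that randomization already deals with this. A reader might infer that a surgeon difference could pass for a block effect. The documents do not support that: allocation is randomized, surgeon can differ between arms only by chance, and the ordinary test allows for chance (0.049 in step 4, even with a large assumed surgeon difference). A systematic imbalance would need a faulty sequence. The protocol does not describe how the sequence is generated, so this can be neither shown nor ruled out. That reply stands, and it limits the point to precision and chance imbalance.

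A reader might also infer that surgeon is unavailable and cannot be adjusted for. That too goes beyond the text. The data come from the medical and anesthesia records, from which surgeon is probably recoverable, and the SAP allows multivariate regression. What the documents support is narrower: surgeon is not listed, and adjustment is not prespecified.

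Three further replies have force. The surgeon effect is assumed, and at 0.3 SD the loss is under one point of power. Port-site infiltration is planned in both arms, and a surgeon term only partly answers its lack of standardization. Surgeon influence on the extraction site, mobilization or discharge is plausible, but the protocol does not state it. None of these replies removes the case for a cheap covariate fixed in advance.

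**Conclusion.** The point holds as a modest improvement in precision. The plan has at least two surgeons, a surgeon-delivered co-intervention that bears on the primary outcome, no surgeon variable, no described balancing, and an unadjusted comparison. On the assumed ranges, ignoring surgeon costs about 1 to 6 points of power and leaves about 2% to 14% of outcome variance unexplained. At 40 patients, a surgeon-share gap of 20 points or more would arise in roughly a quarter to a third of trials, depending on how the arms are formed; at 100 patients this falls to about 6% to 7%. These figures rest on an equal case split and on a surgeon effect for which the documents give no evidence. The planned test remains valid and its estimate unbiased over repeated randomization. This is desirable rather than essential.

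**What to change.** - Add the operating surgeon, taken from the operative record, to the protocol's list of data collected. Do this before publication, because the protocol says the study data are permanently deleted afterwards.
- State in the SAP that the model for 24-hour IV opioid consumption contains arm and surgeon as fixed terms, and likewise for time to ambulation and length of stay. A Mann-Whitney test has no place for a covariate, so where the SAP would use one, name a surgeon-stratified rank test (van Elteren) instead.
- If allocation is not complete, also prepare separate envelope sequences for each surgeon. Always pair them with the surgeon term, for the reason in step 4.

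The covariate works even if allocation has finished. The cost is one data field, one model term and, with two surgeons, one degree of freedom; the optional stratification needs one more envelope set.
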